[figure not shown]

## 2 Introduction

### 2.1 Overview

This protocol proposes to begin Phase 1 of a two phase project to develop and test a multicomponent psychological intervention for caregivers of patients undergoing hematopoietic stem cell transplantation (HCT). During HCT, patients receive high-dose chemotherapy, which is associated with multiple toxicities and leads to burdensome physical symptoms and a prolonged hospitalization. Moreover, during the first 100 days post-transplant while the patient continues to experience many challenging physical symptoms, both patients and their families attend multiple outpatient appointments, manage complex medication schedules, and cope with the uncertainty of the patient's prognosis. Thus, the family and close friends (i.e. caregivers) of patients undergoing HCT are substantially impacted by the patient's illness.

Despite the immense physical and psychological burden experienced by caregivers of patients undergoing HCT, few interventions have been developed to address their needs during the transplant. Prior research on caregivers' intervention has been challenging with many inconclusive or negative studies due to poorly defined interventions that are not specific to a particular population. Thus, there is a critical need to develop population-specific interventions with a sound methodological approach to address the specialized needs of caregivers and provide them with the necessary skills to care for and cope with their loved ones' illness.

We conducted a prospective longitudinal study of patients and caregivers during hospitalization for HCT, which clearly delineated the needs of caregivers during the transplant process. We utilized our data and a systematic review of the literature to develop a preliminary multicomponent psychological intervention to promote effective coping and caregiver well-being. In this proposed project, we will proceed in two phases that incorporate sequential mixed qualitative and quantitative methods. At this time, we are seeking IRB approval for phase 1 procedures only. During phase 1, we will obtain qualitative data from 5-10 caregivers who will participate in the psychological intervention during their loved ones' HCT course to refine the intervention content and schedule to specifically meet the needs of caregivers.

After finalizing the psychological intervention in Phase 1, we will then seek IRB approval to conduct Phase 2 of the project. Phase 2 will only begin after Phase 1 is completed and an amendment has been filed and approved by the IRB. During phase 2, we will conduct a pilot randomized controlled trial of the intervention versus usual care in 100 caregivers to assess the feasibility and preliminary efficacy of the intervention for improving caregiver QOL, mood, caregiving burden, and self-efficacy. The proposed project builds a strong foundation for the development of an innovative psychological intervention that will be tested in a future R01-funded trial.

### 2.2 Background and Significance

#### **Caregivers of patients undergoing HCT experience tremendous burden caring for their loved ones**

HCT is a commonly utilized treatment modality for patients with hematologic malignancies. During HCT, patients receive high-dose chemotherapy, which is associated with multiple toxicities and leads to both burdensome physical symptoms and a prolonged hospitalization. This phase of their illness often carries the highest degree of morbidity as patients cope with symptoms from both their underlying malignancy and from prior therapies. Moreover, during the first 100 days post-transplant while the patient continues to experience many challenging physical symptoms, both patients and their families attend multiple outpatient appointments, manage complex medication schedules, and cope with the uncertainty of the patients' prognosis. Consequently, the family and close friends (i.e. caregivers) of patients undergoing HCT are substantially impacted by the patient's illness. Watching a loved one struggle with the side effects during HCT can be emotionally challenging. Depending on the age and relationship of the caregiver, supporting a loved one through HCT may lead to significant disruptions in the caregiver's personal life, including difficulties in maintaining responsibilities at home and work. Studies have shown that caregivers experience the highest distress immediately before and during their loved ones'

Psychological Intervention to Promote Coping for Caregivers of Patients Undergoing Hematopoietic Stem Cell Transplantation (HCT)  
Protocol version 1/ 10-3-2016

hospitalization for HCT, with subsequent life disruptions seen in the first three months after transplant. Hence, caregivers of patients undergoing HCT are a highly vulnerable population with substantial caregiving burden that results in significant physical and psychological distress.

**Addressing the needs of caregivers is necessary to improve both patients' and caregivers' outcomes**

Caregiving burden often leads to substantial negative effects on caregivers' quality of life (QOL) and mood. In fact, more than a quarter of caregivers of HCT recipients experience significant depression and anxiety symptoms. Fatigue, sleep disturbances, and difficulty maintaining work are common challenges seen in this population. We have conducted a prospective longitudinal study of patients and caregivers during hospitalization for HCT (see preliminary studies), which demonstrates that caregivers experience a substantial decline in QOL and increase in depression symptoms during the HCT process. Hence, addressing the needs of caregivers has the potential to substantially impact their experience and overall QOL. Moreover, as caregivers provide the majority of care for patients undergoing HCT, attending to their needs is an essential step in ensuring the delivery of high-quality care for patients with hematologic malignancies.

**Interventions to promote coping and reduce burden for caregivers of patients undergoing HCT are lacking**

Despite the significant physical and psychological burden experienced by caregivers of patients undergoing HCT, interventions to address their needs during the acute transplantation process are lacking. One study examined the effect of problem-solving intervention for caregivers after patients' hospitalization for HCT. However, the intervention did not address the needs of caregivers immediately before and during the transplant hospitalization, when caregivers report the highest physical and psychological distress. No interventions have been developed to improve caregivers' QOL and mood at their most challenging times during their loved ones' hospitalization for HCT and in the first 100 days post-HCT.

**Developing a population-specific psychological intervention for caregivers is critical to its success**

Based on a number of recent studies, researchers have demonstrated increasing interest in developing population-specific interventions to address the specialized needs of caregivers and provide them with the necessary skills to care for and cope with their loved ones' illness. While the emerging data on caregivers' interventions are encouraging, poorly defined interventions and outcome measures have hampered the field substantially. These methodological shortcomings have resulted in many inconclusive or negative studies, impeding the development of well-conceptualized and sufficiently powered randomized studies.

Research suggests that caregivers of HCT recipients may benefit from a multicomponent psychological intervention to promote effective coping and caregiver well-being. These components include 1) a psycho-educational component to enhance preparedness, manage expectations, and develop caregiving skills; 2) a psychosocial component to promote coping strategies and facilitating acceptance while living with uncertainty; and 3) a self-care component to enhance positive health behaviors and promote their well-being.

**We propose to develop a multicomponent psychological intervention for caregivers during HCT**

Due to the immense caregiving needs during the first 100 days post-HCT, we propose a multi-component psychological intervention for caregivers. We will utilize mixed qualitative and quantitative methods to refine the intervention and to assess its feasibility and preliminary efficacy in improving caregivers' QOL, caregiving burden, mood, and self-efficacy. Our planned intervention is built upon a strong methodological foundation and the findings of a rigorous longitudinal study (see preliminary studies), which described comprehensively the experience patients undergoing HCT and their caregivers during the acute phase of transplantation.

### **Preliminary Studies:**

*QOL and Mood of Patients and Caregivers During Hospitalization for HCT*: We conducted a prospective longitudinal study to investigate the impact of hospitalization for HCT on QOL and mood of patients and caregivers. We enrolled 95% (n =90) of potentially eligible patients undergoing HCT and 70% of their caregivers. We assessed longitudinal QOL and mood both weekly during the transplant hospitalization and at a follow up outpatient clinic visits, with a missing data rate of only 20%. We demonstrated that caregivers' QOL declined over time, with significant decreases in both physical and mental health. Moreover, we showed that caregiver depression symptoms increased dramatically during the HCT hospitalization. This work demonstrates our research team's success in conducting longitudinal studies in patients undergoing HCT and their caregivers. Additionally, the findings from this work were used to develop a palliative care intervention specifically addressing the needs of patients undergoing HCT. Our team utilized the data from this study to develop the psychological intervention targeting the specific needs of this population that we hope to further refine and test in this project.

*Inpatient palliative care integrated with transplant care improves patient-reported outcomes*: Based upon our prior study describing QOL and mood in patients undergoing HCT, we developed a palliative care intervention targeting the specific needs of this population. We enrolled 160 of 186 (86%) eligible patients in 16 months, with only one participant withdrawing from the study. Compared to transplant care, the palliative care intervention led to a rapid and dramatic improvement in patients' QOL, depression, anxiety, and symptom burden. This work highlights our research team's experience conducting supportive care interventions targeted to the specific needs of the population, and our ability to successfully recruit and enroll patients with hematologic malignancies for intervention studies.

### **3 Objectives**

The objective for Phase 1 of the study is described below.

**Objective 1:** To refine a multicomponent psychological intervention to promote effective coping and reduce caregiving burden of FC of patients undergoing HCT.

### **4 Research Subject Selection**

#### **4.1 Study Subject Selection:**

During phase 1, we will use qualitative data to refine the multicomponent psychological intervention specifically targeting the needs of caregivers during their loved ones' hospitalization for HCT and in the first 100 days post-HCT. We will recruit 5-10 adult caregivers of patients undergoing HCT at MGH to participate in phase 1 of this project. Caregivers will be recruited during the patient transplant consent visit, which typically occurs 2-4 weeks prior to admission for HCT. Caregivers are required to attend the HCT consent visit with the patient.

#### *Caregivers Eligibility Criteria:*

- 1) Adult caregivers ( $\geq 18$  years) of patients undergoing HCT at MGH.
- 2) A relative or a friend who either lives with the patient or has in-person contact with him or her at least twice per week and is identified as the primary caregiver for transplant
- 3) Ability to speak English or able to complete questionnaires with minimum assistance of an interpreter.

#### *Caregivers Exclusion Criteria:*

- 1) Significant uncontrolled psychiatric disorder (psychotic disorder, bipolar disorder, major depression) or other co-morbid disease (dementia, cognitive impairment), which the treating clinician believes prohibits the ability to participate in study procedures.

## **5 Research Subject Entry**

### **5.1 Study Research Subject Entry**

A total of 5-10 caregivers of patients undergoing HCT will participate in phase 1 of this study. The research team will review the transplant clinic schedule to identify potentially eligible caregivers for study participation. We will approach caregivers to participate in phase 1 during the outpatient clinic visit when their loved ones' consent for HCT, which typically occurs 2-4 weeks prior to HCT. Patients are required to be accompanied by a caregiver for the consent visit. The research team will contact eligible participants' oncology clinicians to inform them that we plan to approach the caregiver and inquire about any concerns regarding their participation. If the clinician objects to the caregivers' participation, we will document the reason and not approach those individuals.

If the oncologist has no concerns regarding the caregivers' participation, the research staff will approach eligible caregivers immediately after the transplant consent clinic visit. The research assistant (RA) will review the consent form with potential participants, which will clearly detail the nature of the study procedures and the time requirement. The RA will obtain written informed consent from participants and provide them with a copy of the signed consent form.

Enrolled caregivers will complete a baseline self-report questionnaire (Appendix A) at the time of obtaining informed consent for the study or within the 72-hour window from study enrollment. Caregivers who provide informed consent and complete the baseline questionnaire will then be registered with ODQ and scheduled for their first study intervention visit either in-person or via telephone. The RA will be responsible for contacting ODQ. The ODQ will require a copy of the caregivers' informed consent and eligibility checklist.

## **5.2 REGISTRATION PROCEDURES**

### **5.2.1 Registration process for DF/HCC and DF/PCC Institutions Registrations**

After completion of baseline questionnaires, caregivers will be registered centrally with the DF/HCC Office of Data Quality (ODQ) central registration system. Registration Process for DF/HCC Institutions DF/HCC Standard Operation Procedures for Human Subject Research Titled Subject Protocol Registration (SOP# REGIST-101) must be followed. For each study participant, we will complete the following registration procedures:

- We will obtain written informed consent from the participant prior to the performance of any protocol specific procedures or assessments.
- We will complete the ODQ protocol-specific eligibility checklist using the eligibility assessment documented in the research chart. Only eligible participants will be registered. To be eligible for registration to the protocol, the participant must meet all including and exclusion criterion as described in this protocol and reflected on our eligibility checklist.
- We will fax the eligibility checklist(s) and all pages of the consent form(s) to the ODQ at [contact].
- The ODQ Registrar will a) review the eligibility checklist, b) register the participant on the protocol, and c) randomize the participant when applicable.
- An email confirmation of the registration will be sent to the Overall PI, study coordinator(s), treating investigator, and registering person immediately following the registration.

We are requesting a a HIPAA Waiver of Alteration to Use or Disclose of Protected Health Information from the IRB. This waiver is being requested to identify potential participants from a minimal chart review.

Psychological Intervention to Promote Coping for Caregivers of Patients Undergoing Hematopoietic Stem Cell Transplantation (HCT)  
 Protocol version 1/ 10-3-2016

In accordance with the DF/HCC policy, this Waiver: (1) is being sought solely to review Protected Health Information as necessary to prepare a research protocol, (2) will not include removing Protected Health Information from the Covered Entity by the researcher, and (3) the Protected Health Information for which we are requesting access is necessary for the research purposes.

**5.2.2 Registration Process for Other Investigative Sites: Not applicable**

**5 Study Design and Methods**

**5.1 Design/ Study Type**

During phase 1, we will use qualitative data to refine a multicomponent psychological intervention specifically targeting the needs of caregivers’ during their loved ones’ hospitalization for HCT and in the first 100 days after transplant.

**Phase 1 Intervention Refinement:** We utilized the findings from our longitudinal study and a thorough review of the literature to identify the necessary components of our planned caregiver intervention, as depicted in Table 1. The preliminary content includes three essential components: 1) a psychoeducational component to address preparedness, manage expectations, and develop caregiving skills; 2) a psychosocial component focusing on coping strategies, mindfulness, and facilitating acceptance while living with uncertainty; and 3) a self-care component to promote caregiver health and well-being. We anticipate that the psychological intervention will consist of eight individual sessions (30-45 minutes each) starting prior to admission for HCT and continuing until day + 70 after HCT, which will provide sufficient dose to promote effective coping and reduce caregiving burden. We will coordinate sessions with hospital and clinic visits or conduct them via phone to minimize participant burden and facilitate adherence. [name] (a behavioral psychologist and researcher) will deliver the intervention. [name] has extensive experience as a therapist on NIH-funded trials. During phase 1, we will refine the intervention based on qualitative interviews and feedback from 5-10 caregivers who will attend the psychological intervention sessions. We will then finalize the study intervention manual, which will be used in phase 2.

Session	Behavioral Target	Skill Area	Topics
1	Introduction	Psychoeducation	
 
➤ Introduce intervention purpose and goals
 
➤ Explore how FC cope with the HCT process
 
➤ Manage expectations for HCT, acknowledge and normalize fears
 

2,3	Coping & managing emotions	Psychosocial	
 
➤ Explore strategies for balancing acceptance and change-oriented coping approaches.
 
➤ Introduce mindfulness to observe the HCT experience (thoughts, feelings, loved ones’ symptoms) in an objective, nonjudgmental fashion
 
➤ Explore the use of mindfulness to cope with HCT-related uncertainty
 
➤ Identify ways to support loved ones during HCT hospitalization
 

4,5	Preparedness & caregiving skills	Psychoeducation	
 
➤ Identify caregiving needs in the immediate post-HCT period
 
➤ Help FC gain more confidence in responding to physical and psychosocial issues post-HCT
 
➤ Elevate FC sense of self-efficacy
 
➤ Enhance FC communication with the health care team
 

6	Healthy behaviors & self-care	Self-care	
 
➤ Identify and explore FC needs
 
➤ Introduce strategies for stress management, and promotion of self-care behaviors (sleep, healthy diet, exercise, and seeking support)
 

7	Interpersonal relationship	Psychosocial	
 
➤ Identify attitudes and beliefs about FC relationship to the patient
 

Psychological Intervention to Promote Coping for Caregivers of Patients Undergoing Hematopoietic Stem Cell Transplantation (HCT)  
 Protocol version 1/ 10-3-2016

			
 
➤ Identify differences between assertive, passive, aggressive behaviors
 
➤ Introduce strategies to encourage relationship-enhancing behaviors
 

8	Program overview	All	
 
➤ Summarize and review main content of the intervention
 
➤ Address additional challenges and problems
 
➤ Brainstorm strategies to maintaining use of skills over time.
 

**Utilizing data from phase 1 to refine the intervention:** We will utilize the qualitative data obtained from phase 1 and clinicians’ experience to finalize the multicomponent psychological intervention. Specifically, we will refine the following aspects of the intervention:

- **Intervention content:** We will use caregivers’ feedback to confirm the relevance of the intervention content, and to revise content as needed. For instance, if caregiver report that they would have liked to focus on more active coping strategies, we will increase the balance between change- and acceptance-oriented (e.g., mindfulness) approaches. To further enhance the intervention, we also may integrate caregivers’ real-life concerns as examples throughout the protocol when introducing the use of coping skills and strategies.
- **Program structure and schedule:** We anticipate that caregivers will have different needs during their loved ones’ hospitalization for HCT vs. the immediate post-transplant period. However, we will use caregivers’ feedback to guide the order and timing of the eight intervention sessions during these two periods. Additionally, we may revise session number (8 sessions) or length (30-45 min per session) based on caregivers’ feedback about participation burden and utility.
- **Program modality:** We will use exit interview data to determine whether the delivery of the intervention visit in-person or over the phone was acceptable to participants.
- **Additional areas of concern:** We will identify any additional areas of concern from caregivers that were not addressed specifically in the intervention and integrate them in a revised intervention manual.

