- **Program structure and schedule:** We anticipate that caregivers will have different needs during their loved ones' hospitalization for HCT vs. the immediate post-transplant period. However, we will use caregivers' feedback to guide the order and timing of the eight intervention sessions during these two periods. Additionally, we may revise session number (8 sessions) or length (30-45 min per session) based on caregivers' feedback about participation burden and utility.
- **Program modality:** We will use exit interview data to determine whether the delivery of the intervention visit in-person or over the phone was acceptable to participants.
- **Additional areas of concern:** We will identify any additional areas of concern from caregivers that were not addressed specifically in the intervention and integrate them in a revised intervention manual.

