## INTRODUCTION

You recently took part in a study that was designed to help caregivers of patients undergoing hematopoietic stem cell transplantation (HCT) cope most effectively with their loved ones' illness. We are now interested to know about your satisfaction with different aspects of this research study so that we continue to shape how to provide it to patients. There is no right or wrong answer. Your answers will be kept confidential and will not affect your participation in future research studies or your access to medical care.

First, I am going to ask you some questions about the timing of the sessions you had and how they were delivered.

1. This study was scheduled to start 1-2 weeks prior to HCT. How do you feel about the timing of the program?

- A. Right time
- B. Too soon before transplant
- C. Too close to time of transplant

Additional Comments:

2. This study was scheduled to continue through day +70 after HCT. How do you feel about the timing of the program?

- A. Right time
- B. Too short after HCT
- C. Too long after HCT

Additional Comments:

3. The research study was designed so that sessions were scheduled along with your other medical appointments whenever possible. How do you feel about the convenience of attending the sessions?

- A. Convenient
- B. Not convenient
- C. Not sure

Additional Comments:

Psychological Intervention to Promote Coping for Caregivers of Patients Undergoing Hematopoietic Stem Cell Transplantation (HCT)  
Protocol version 1/ 10-3-2016

4. What prevented you from attending the intervention sessions? What would help you attend more of these sessions?

5. The research study was designed so that sessions can be scheduled over the phone when in-person visits were not possible. How do you feel about the phone sessions?

- A. Great
- B. In-person was better
- C. Not sure

Additional Comments:
----------------------

Additional Probe: Would you have preferred all sessions to be delivered over the telephone for convenience?

6. How do you feel about the total number of visits included in this research study (eight visits total)?

- A. Right amount
- B. Too few
- C. Too many

Additional Comments:
----------------------

7. How do you feel about the amount of time each visit lasted?

- A. Right amount
- B. Too short
- C. Too long

Additional Comments:
----------------------

Now I am going to ask you some questions about the material covered in your visits.

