8. During these sessions, you may have learned about strategies to help you cope most effectively with your loved ones' illness. How helpful did you find these strategies?

- A. Helpful
- B. Not helpful
- C. Not sure

Additional Comments:
----------------------

Additional Probe: The interviewer can remind the caregiver about specific strategies such as acceptance, mindfulness, problem-solving, self-care, communication techniques, etc. Also ask which of these strategies was the most helpful

Psychological Intervention to Promote Coping for Caregivers of Patients Undergoing Hematopoietic Stem Cell Transplantation (HCT)  
Protocol version 1/ 10-3-2016

9. Since going to the study visits, how often have you used any of these strategies on your own?

- A. Daily
- B. Few times/ week
- C. Once or twice
- D. Never

Additional Comments:

10. During these sessions, you may have learned about skills or strategies that would help you gain more confidence in your ability to care for your loved one. How helpful was it to learn about these skills or strategies?

- A. Helpful
- B. Not helpful
- C. Not sure

Additional Comments:

Additional probe: Which of these strategies was the most helpful?

11. Since going to the study visits, how often have you used any of the skills or strategies on your own?

- A. Daily
- B. Few times/ week
- C. Once or twice
- D. Never

Additional Comments:

12. During these sessions, you may have learned about skills or strategies that would help take better care of yourself during your loved ones' illness. How helpful was it to learn about these skills or strategies?

- A. Helpful
- B. Not helpful
- C. Not sure

Additional Comments:

Additional probe: Which of these strategies was the most helpful?

Psychological Intervention to Promote Coping for Caregivers of Patients Undergoing Hematopoietic Stem Cell Transplantation (HCT)  
Protocol version 1/ 10-3-2016

13. Since going to the study visits, how often have you used any of the skills or strategies on your own?

- A. Daily
- B. Few times/ week
- C. Once or twice
- D. Never

Additional Comments:

14. During these sessions, you may have learned about skills or strategies that would help communicate more effectively with your loved one. How helpful was it to learn about these skills or strategies?

- A. Helpful
- B. Not helpful
- C. Not sure

Additional Comments:

Additional probe: Which of these strategies was the most helpful?

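### Caregiver feedback is meant to guide the order and timing of the eight sessions, but the exit interview guide has no item on order and asks about timing only for the program's start and end

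*Combined protocol and SAP*

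**What the plan says.** Section 7.1.1 makes the Phase 1 primary endpoint a final version of the intervention, resting on the qualitative analysis. Section 5.1 lists what will be refined, and Section 7.3 repeats the list. On content, caregiver feedback is to "confirm the relevance of the intervention content, and to revise content as needed". On structure, the plan commits to using caregivers' "feedback to guide the order and timing of the eight intervention sessions during these two periods". It adds that session number and length may be revised, and that interview data will show whether in-person or phone delivery was acceptable.

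Section 5.2 (study instruments) describes a semi-structured exit interview of about 30 minutes, with probes, and says participants complete no further study instruments. The guide in Appendix B has 22 items. Its two timing items read "This study was scheduled to start 1-2 weeks prior to HCT. How do you feel about the timing of the program" and "This study was scheduled to continue through day +70 after HCT. How do you feel about the timing of the program".

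The session table in Section 5.1 gives session 1 the topic "Manage expectations for HCT, acknowledge and normalize fears" and sessions 4-5, among four topics, "Enhance FC communication with the health care team". The guide's one dedicated communication item, item 14, concerns "skills or strategies that would help communicate more effectively with your loved one".

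**The concern.** A refinement study can act only on what it asks or happens to hear. Order is a stated target in two sections. The plan expects needs to differ between the admission and the period after it, so where each session falls is a real design question for the Phase 2 manual. If no one is asked, the final order may rest on scattered volunteered remarks and on clinicians' views, while the plan says that caregivers' feedback guided it. With 5 to 10 caregivers and one exit interview each, an unasked question is hard to recover later.

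**Working it through.** The plan gives no figure on this point, so the check is a comparison of stated targets with the items of the guide.

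**Structure and delivery targets (Sections 5.1 and 7.3) against Appendix B**

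| Target | Items that ask about it | Coverage |
|---|---|---|
| Order of sessions | none | none |
| Timing of sessions | 1 (program start), 2 (program end) | the two ends only |
| Number of sessions | 6 | direct |
| Session length | 7 | direct |
| In-person or phone delivery | 5, 21 | direct |

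Of five targets, three are asked about directly, one in part and one not at all. Items 3 and 4 concern convenience and barriers to attendance. Items 18 to 20 ask, for three periods, what other programs would have helped; they do not ask about the sequence of this one.

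**Content by session (Section 5.1 table) against Appendix B**

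| Session | Items |
|---|---|
| 1, introduction | none dedicated; the topic of how caregivers cope overlaps item 8 |
| 2-3, coping | 8, 9 |
| 4-5, preparedness and caregiving skills | 10, 11; the health care team is not named |
| 6, self-care | 12, 13 |
| 7, relationship with the patient | 14, 15 |
| 8, review | none dedicated |

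Items 16, 17 and 22 are open and could draw a remark on any of these. The probe under item 8 mentions communication techniques without saying with whom. The items run from 1 to 22 without a break in numbering, so the gaps do not look like lost text.

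**Cost of an added item.** Average time per item is 30 / 22 = 1.4 minutes. One open question therefore costs about 1 to 2 minutes. If both optional probes also ran as long as an average item, the total would be 3 x 1.4 = about 4 minutes. That is an upper figure, since a probe is shorter than an item.

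**The case against.** The strongest reply is that this is a semi-structured interview and not a checklist. Section 5.2 provides for probes, interviewer training, mock interviews and supervision of the first two interviews. Such a guide does not need an item for every topic. Items 16 and 17 follow directly on the content block and ask what else was or was not helpful. Items 18 to 20 give needs by period, which bear on where content belongs.

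For content, this reply largely stands. Item 10 and its probe cover the sessions 4-5 module as a whole, and the item 8 probe can bring up communication of any kind. Part of session 1 overlaps item 8. Other listed topics also lack an item of their own, as does the whole of session 8. A reader might infer that session 1 and communication with the health care team would enter the Phase 2 manual unexamined. The documents do not support that: probes and open items can reach both, and Section 5.1 adds clinicians' experience as an input. Nor does any section treat silence as approval.

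A reader might also call the exit interview the only source of caregiver feedback. Section 5.1 speaks of interviews and feedback, so the safe statement is that it is the only feedback instrument described.

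For order, the reply does not remove the gap. No item or scripted probe raises the subject, and items 18 to 20 ask about other programs. An interviewer may think to ask, but nothing in the guide makes the question uniform across caregivers.

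**Conclusion.** The point holds for session order, and in part for timing: one of five stated structure and delivery targets has no item, and a second is asked about only at the program's start and end. This rests on the guide as printed and on the absence of any other described instrument. It does not mean that feedback on order is impossible, only that the plan does not directly collect it. The two content gaps are real as wording but minor, and closed items for them would be a matter of preference.

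It is tempting to attach a probability. If each caregiver volunteered a remark independently with probability p, the chance that nobody does so is (1 - p)^n. For n = 5 and n = 10 this gives:

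- p = 10%: 59% and 35%
- p = 20%: 33% and 11%
- p = 30%: 17% and 3%
- p = 50%: 3% and 0.1%

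The documents give no value of p, and the formula treats every caregiver as having a view. The range is too wide to carry weight, and the conclusion does not depend on it.

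**What to change.** Add one open question to Appendix B, next to item 2 or item 6. For example: *Thinking back over the eight sessions, which sessions or topics, if any, would you have moved earlier or later: before admission, during the hospital stay, or after discharge?* This covers order and also the timing between the program's two ends.

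Optionally, add two scripted probes: one under item 8 on the session 1 material about expectations and fears, and one under item 10 or item 14 on communicating with the health care team. A prompt has some value for session 1 because of recall. Section 5.5.1 puts the interview at day +90, give or take 15 days. If session 1 took place at the start named in item 1, it lies 75 + 7 = 82 to 105 + 14 = 119 days back.

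Keep items 9, 11, 13 and 15 as they are. Merging them would save time but lose data on use by skill area, which bears on revising content.

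The cost is a short edit to Appendix B before first use and about 1 to 2 minutes per interview.
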